9.2.6. Secondary Endpoint Analyses

Secondary endpoints will be analyzed to evaluate for change from Screening Visit B (Visit 2) to the level at Week 16 (Visit 10). Change from Screening level will be the dependent variable. The secondary endpoints include letters of BCVA or LLVA, improvement in visual field area and microperimetry, and increase in dark-adapted flash b-wave amplitudes.

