3. INVESTIGATIONAL PLAN

3.1. Overall Clinical Trial Design and Plan

In this open-label, non-comparator Phase II clinical trial, 8 (eight) evaluable subjects with retinitis pigmentosa due to rhodopsin mutations (including P23H) will be identified and treated with serial intravitreal injections of ADX-2191 in the worse seeing eye (“**the study eye**”). Ocular structure and function will be evaluated.

The first four subjects (Cohort A) will be treated with monthly intravitreal injections of ADX-2191 for a total of three injections; the last four subjects (Cohort B) will be treated with twice monthly intravitreal injections of ADX-2191 for a total of six injections. All subjects will be followed for a total of 16 weeks following dosing.

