6.6. Urine pregnancy testing

For women of childbearing potential (WOCBP), a urine pregnancy test will be collected at the Screening Visit B (Visit 2), and prior to each injection of ADX-2191, through Visit 8 / Week 10. Results must be available and confirmed to be negative before the subject may be enrolled in the clinical trial. IP must be discontinued for any subject with a positive pregnancy test result.

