6.8. Investigational Product Intravitreal Injection

Upon completion of the final screening tests at Visit 2, subjects will receive ADX-2191 400 µg/0.05 mL intravitreal injection to the study eye, in accordance with the schedule of events (Table 1). The study eye will be the subject's worse seeing eye. Subjects who are scheduled to receive an intravitreal injection at Weeks 0 (V2), Week 4 (V5), or Week 8 (V7) following completion of testing.

Intravitreal ADX-2191 injections will be performed aseptically after the topical application or subconjunctival injection of an anesthetic agent and 5% povidone iodine to the conjunctiva. Each patient will receive an intravitreal injection of 400 µg/0.05 mL ADX 2191, 3.0 mm posterior to the limbus with a 33-gauge or similar needle.

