7.8. Week 10 (Visit 8)—Cohort B only

- Perform Corneal Slit Lamp Safety Exam (Section 6.7.9)
- Collect samples for urine pregnancy test, if applicable (Section 6.6)
- Investigational Product Intravitreal Injection (Section 6.8)
- Prescribe artificial tears and/or lubricating ointment (Section 6.9)
- Collect concomitant medications (Section 6.4)
- Collect adverse events (Section 6.5)

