7.9. Week 12 (Visit 9)

- Perform BCVA (Section 6.7.1)
- Perform LLVA (Section 6.7.2)
- Perform Full Ophthalmic Examination (Section 6.7.7)
- Collect Wide Field Color and Autofluorescence Fundus Photographs (Section 6.7.8)
- Collect Macular Optical Coherence Tomography (Section 6.7.6)
- Collect Dark-Adapted Chromatic Perimetry (Section 6.7.5)
- Collect Macular Integrity Assessment (MAIA) (Section 6.7.3)
- Collect concomitant medications (Section 6.4)
- Collect adverse events (Section 6.5)
- Collect Full-field electroretinography (ERG) (Section 6.7.4)

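### Section 9.2.6 names only the change to Week 16, nominally 8 weeks (Cohort A) or 6 weeks (Cohort B) after the last injection: it gives no end-of-dosing reading for five secondary endpoints and cannot be carried out for ERG

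*Combined protocol and SAP*

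**What the plan says.** Section 9.2.6 sets a single contrast for efficacy: "Secondary endpoints will be analyzed to evaluate for change from Screening Visit B (Visit 2) to the level at Week 16 (Visit 10". It then adds: "The secondary endpoints include letters of BCVA or LLVA, improvement in visual field area and microperimetry, and increase in dark-adapted flash b-wave amplitudes". No other visit is named. Section 2.2.2 lists six secondary endpoints and gives none of them a time point. OCT is not in the 9.2.6 list, but it is one of the six and so falls under the general sentence.

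Section 3.1 gives the regimens: "The first four subjects (Cohort A) will be treated with monthly intravitreal injections of ADX-2191 for a total of three injections", and "the last four subjects (Cohort B) will be treated with twice monthly intravitreal injections of ADX-2191 for a total of six injections". Table 1 puts the Cohort A injections at Weeks 0, 4 and 8, and Section 6.8 names the same visits, "Weeks 0 (V2), Week 4 (V5), or Week 8 (V7) following completion of testing". Cohort B is injected at Weeks 0, 2, 4, 6, 8 and 10. Section 7.8 lists the Week 10 injection, and Section 6.6 requires pregnancy testing "prior to each injection of ADX-2191, through Visit 8 / Week 10".

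On collection, BCVA, LLVA, MAIA and DAC perimetry are measured at V1, V2, V3, V5, V7, V9 and V10 (Sections 6.7.1 to 6.7.3 and 6.7.5). OCT is measured at V1, V5, V7, V9 and V10 (Section 6.7.6). ERG is measured at V1 and V9 only (Section 6.7.4). Section 7.9 lists for Week 12 "Collect Full-field electroretinography (ERG) (Section 6.7.4", and Section 7.10 has no ERG line for Week 16.

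Sections 9.2.1 and 9.2.8 leave the final statistical procedures to an SAP completed before database lock. Analyses added to it afterwards are to be labelled post hoc.

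**The concern.** Section 2.1 asks about the efficacy of repeated injections. The one contrast that 9.2.6 names is taken after dosing has stopped, at the last visit of follow-up, and no reason for choosing that visit is given.

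Two interpretations are then closed off for the five endpoints measured at Week 16. If the change is null, the named analysis cannot say whether the drug did nothing or whether an effect had faded. If a change is present, there is no end-of-dosing value to set it against, so nothing can be said about how well it lasted.

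For ERG the problem is different and does not depend on any view about waning. 9.2.6 names the b-wave amplitude, yet the schedule provides neither the V2 baseline nor the V10 value that the rule needs.

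**Working it through.** **Dose counts.** Weeks are counted from Visit 2, which Section 7 defines as Week 0 and at which the first injection is given.
- Cohort A: Weeks 0, 4, 8 = 3 injections, interval 4 weeks, last dose Week 8.
- Cohort B: Weeks 0, 2, 4, 6, 8, 10 = 6 injections, interval 2 weeks, last dose Week 10.

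Both counts reproduce the totals in Section 3.1.

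**Time since last injection.** Gap = assessment week − last-dose week; number of intervals = gap ÷ dosing interval. Table 1 allows ±5 days at each visit from Week 6 on, so the gap can move by ±10 days.

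| Cohort | Visit | Nominal gap | Intervals | Gap within windows | Intervals within windows |
|---|---|---|---|---|---|
| A | Week 12 | 12 − 8 = 4 wk | 4/4 = 1.0 | 18–38 days | 0.64–1.36 |
| A | Week 16 | 16 − 8 = 8 wk | 8/4 = 2.0 | 46–66 days | 1.64–2.36 |
| B | Week 12 | 12 − 10 = 2 wk | 2/2 = 1.0 | 4–24 days | 0.29–1.71 |
| B | Week 16 | 16 − 10 = 6 wk | 6/2 = 3.0 | 32–52 days | 2.29–3.71 |

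Table 1 footnote 5 puts injections after all other assessments. The Week 4 and Week 8 readings therefore also come nominally one interval after the preceding dose. Week 12 continues that series after the full course; Week 16 does not.

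**Can the 9.2.6 rule be applied?**

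| Endpoint | V2 baseline | Week 12 (V9) | Week 16 (V10) |
|---|---|---|---|
| BCVA, LLVA, MAIA, DAC | yes | yes | yes |
| OCT | no (V1 only) | yes | yes |
| ERG | no (V1 only) | yes | no |

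V9 is the only post-dose visit with all six endpoints. Footnote 6 of Table 1, which designates V2 results for quantitative analysis, is attached only to BCVA, LLVA, DAC and MAIA.

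**How much could timing matter? (assumption)** The documents give no waning rate. For illustration, suppose the effect decays exponentially after the last dose with half-life h weeks. Share left = 0.5^(gap/h).

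| h (weeks) | A, Week 12 | A, Week 16 | B, Week 12 | B, Week 16 |
|---|---|---|---|---|
| 1 | 6% | 0.4% | 25% | 1.6% |
| 2 | 25% | 6% | 50% | 12.5% |
| 4 | 50% | 25% | 71% | 35% |
| 8 | 71% | 50% | 84% | 59% |

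If the effect does not wane, all entries are 100% and the choice of visit costs nothing.

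**Does Week 12 equalise the cohorts?** No. Cohort A is 2 weeks further from its last dose at both visits (4 − 2 = 8 − 6 = 2). Under the same model the B:A ratio is 0.5^(−2/h), which is 4.0, 2.0 and 1.4 for h = 1, 2 and 4, identical at Week 12 and Week 16. The B − A difference is larger at Week 12: 18.8, 25.0 and 20.7 percentage points, against 1.2, 6.3 and 10.4 at Week 16.

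**How informative is a null at all?** No power calculation is given. For a one-sample t-test of change (assumed; two-sided 0.05, 80% power), the detectable mean change is about 1.16 SD with n = 8 and 2.13 SD with n = 4.

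**The case against.** The strongest reply has four parts.

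First, waning is conjecture. Section 1.1 describes clearance of a misfolded protein in a progressive degeneration, and nothing says whether benefit would be brief or lasting. An end-of-study reading is a legitimate choice. This stands: a reader might infer that Week 16 will miss a real effect, and the documents do not support that. What remains is that the named analysis cannot tell the possibilities apart.

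Second, the data exist. Five endpoints are measured at Weeks 4, 8 and 12 as well, Section 9.2.1 provides for descriptive summaries without limiting them to V10, 9.2.6 does not forbid other time points, and the SAP governs. This also stands, and it makes the gap one of specification rather than design. It is not a full answer, because an end-of-dosing contrast left out of the SAP would be post hoc under Section 9.2.8.

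Third, a reader might infer that Week 12, being one dosing interval after the last dose in both cohorts, gives a fair comparison of regimens. It does not. The equality is nominal, with windows of 0.64–1.36 intervals in A and 0.29–1.71 in B, and the 2-week difference in time off drug is the same at both visits. The trial also has no comparator, and 9.2.6 plans no between-cohort contrast.

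Fourth, efficacy is secondary to safety, and with 8 subjects a null is weak at any visit. That is correct and limits the importance of the point. It has no bearing on the ERG contradiction.

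**Conclusion.** The point holds in a limited form. For BCVA, LLVA, microperimetry, DAC perimetry and OCT, Section 9.2.6 gives only an off-treatment reading, nominally 8 weeks (A) and 6 weeks (B) after the last injection, and names no end-of-dosing reading. A null there is ambiguous, and a persisting change cannot be described as durable. Any loss of effect at Week 16 depends on a waning rate that the documents do not give: under the assumed half-lives of 1 to 8 weeks, the share left runs from 0.4% to 50% in A and from 1.6% to 59% in B.

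A reader might infer that all efficacy is read only at Week 16. That is untrue of ERG, whose sole post-dose measurement is already Week 12. ERG escapes the washout question, but 9.2.6 cannot be executed for it, and Sections 6.7.4 and 9.2.6 must be reconciled. OCT lacks the V2 baseline that the rule requires. These two mismatches need no assumption.

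The change is worth making because it is cheap and the SAP is still to be finalised. With efficacy secondary and 8 subjects, it does not threaten the trial's primary purpose.

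**What to change.** In Section 9.2.6 and in the SAP, before database lock:

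- Name change to Week 12 (V9) as the end-of-dosing reading for all six secondary endpoints.
- Name change to Week 16 (V10) as the off-treatment reading for the five endpoints measured then, and state that ERG has none.
- State the baseline for each endpoint: V1 for ERG and OCT, V2 for BCVA, LLVA, MAIA and DAC perimetry.
- Present both time points by cohort, labelled descriptive, with actual days since last injection. Actual days are needed because of the visit windows, and because Section 3.6 moves the Week 16 visit to the time of discontinuation for subjects who stop treatment early.
- Interpret a null Week 16 result only alongside Week 12. Make no claim that Week 12 separates the regimens free of confounding, or that it makes a null conclusive.

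The cost is wording and one more column per table. No new visit, test or subject is needed. The downside is one additional reported time point, which is why the descriptive label matters.

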2.2.2. Secondary Endpoints

The secondary endpoint include:

- 1) Best Corrected Visual Acuity (BCVA): Change in BCVA will be assessed using a normally illuminated ETDRS (Early Treatment Diabetic Retinopathy) chart.
- 2) Low-luminance visual acuity (LLVA): Change in Low-luminance visual acuity (LLVA) and the low luminance deficit (LLD) will be assessed. The LLD is defined as the difference between the BCVA and LLVA. LLVA will be assessed using a 2.0 log unit neutral density filter while reading a normally illuminated ETDRS (Early Treatment Diabetic Retinopathy) chart.
- 3) Macular Integrity Assessment (MAIA) Microperimetry: Central retinal sensitivity will be assessed using MAIA microperimetry using a standard 10-2 test grid with a Goldman size III stimulus of various intensities presented on a mesopic background (4 apostilbs).
- 4) Full field Electroretinography (ffERG): Change in dark-adapted flash ($0.01 \text{ cd} \cdot \text{s} \cdot \text{m}^{-2}$) b-wave amplitudes will be analyzed. Testing will be performed using a standard International Society for Clinical Electrophysiology of Vision (ISCEV) protocol.
- 5) Dark-Adapted Chromatic Perimetry: Change in dark adapted retinal sensitivity (dB) to the blue and red stimuli on the Medmont Dark-Adapted Chromatic (DAC) perimeter will be assessed.
- 6) OCT: Change in Central Subfield Foveal Thickness (CSFT) and Change in Ellipsoid Zone (EZ) area/width will be assessed using a spectral domain optical coherence tomograph (SD-OCT) volume scan using the Heidelberg Spectralis.

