6.7.4. Full Field Electroretinography

A standard full-field electroretinogram (ERG) will be performed. Change in dark-adapted flash (0.01 cd•s•m⁻²) b-wave amplitudes will be analyzed. Testing will be performed using a standard

International Society for Clinical Electrophysiology of Vision (ISCEV) protocol. Both eyes will be evaluated. ERG will be collected at Visits V1 and V9.

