6.7.6. Macular Spectral-Domain Optical Coherence Tomography (SD-OCT)

Macular SD-OCT imaging will be done; the Heidelberg Spectralis is preferred. Both eyes will be imaged at Visits V1 and V10. The macular volume scan should be obtained using the preset “Posterior Pole settings: **Scan Extent:** Volume Scan (30° x 25°); **Scan Sections/B-scans:** 61 sections (with a 120 µm spacing); **Resolution:** High Speed with an ART mean of at least 9 frames. SD-OCT will be collected at Visits V1, V5, V7, V9, and V10. Both eyes will be evaluated at visits V1, V9, V10 and only the study eye will be evaluated at V5 and V7.

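### The Visit 2 to Visit 10 rule for secondary endpoints in Section 9.2.6 cannot be computed for ffERG as scheduled, and it fits OCT and perimetry poorly

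*Combined protocol and SAP*

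**What the plan says.** Section 9.2.6 states the analysis of the secondary endpoints in three sentences. The first sets the visits: "Secondary endpoints will be analyzed to evaluate for change from Screening Visit B (Visit 2) to the level at Week 16 (Visit 10"). The second is looser: "Change from Screening level will be the dependent variable". It does not say which of the two screening visits is meant. The third lists what the endpoints include: letters of BCVA or LLVA, then "improvement in visual field area and microperimetry, and increase in dark-adapted flash b-wave amplitudes".

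The assessment sections give the visits at which each measure is taken. Section 6.7.4 says "ERG will be collected at Visits V1 and V9". Section 6.7.6 says "SD-OCT will be collected at Visits V1, V5, V7, V9, and V10". Table 1 and the visit lists in Sections 7.1 to 7.10 agree with both.

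Section 2.2.2 lists six secondary endpoints. The fifth, on the Medmont DAC perimeter, is "Change in dark adapted retinal sensitivity (dB) to the blue and red stimuli". The sixth is OCT: "Change in Central Subfield Foveal Thickness (CSFT) and Change in Ellipsoid Zone (EZ) area/width will be assessed".

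**The concern.** An analysis rule should name visits at which the measure is taken, and a quantity that the endpoint section defines. For ffERG, Section 9.2.6 names a baseline visit and a final visit at which no ERG is scheduled. For OCT it names a baseline visit with no scan, and it then leaves OCT off its list. For perimetry it names an area where the endpoint is a sensitivity.

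Efficacy is part of the objective in Section 2.1, and the secondary endpoints carry it. The background in Section 1.1 cites improved ERG responses in P23H rodents alongside clearance of misfolded rhodopsin, so ffERG is one of the measures closest to the rationale. The trial is open-label, and Section 9.2.8 requires the SAP to be final only before database lock. Any visit or scale that the protocol leaves open could therefore be settled after results have been seen. With eight subjects, that could affect how a secondary result reads.

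**Working it through.** No sample-size or power figure bears on this point, and the target of 8 subjects (4 per cohort, Section 3.1) has no stated derivation to reproduce. The check is a comparison of the rule with the schedule.

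**Step 1: visits and scheduled pairs.** The inputs are the visits in Table 1 and Sections 6.7.1 to 6.7.6. For a change from visit a to visit b, the number of scheduled pairs is 8 if both visits are scheduled for that measure, and 0 otherwise.

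| Endpoint in 2.2.2 | Scheduled visits | V2 to V10 | V1 to V10 | V1 to V9 | Named in 9.2.6 |
|---|---|---|---|---|---|
| BCVA | V1, V2, V3, V5, V7, V9, V10 | 8 | 8 | 8 | yes |
| LLVA and LLD | V1, V2, V3, V5, V7, V9, V10 | 8 | 8 | 8 | LLVA yes, LLD no |
| MAIA | V1, V2, V3, V5, V7, V9, V10 | 8 | 8 | 8 | yes |
| ffERG | V1, V9 | 0 | 0 | 8 | yes |
| DAC perimetry | V1, V2, V3, V5, V7, V9, V10 | 8 | 8 | 8 | no |
| OCT | V1, V5, V7, V9, V10 | 0 | 8 | 8 | no |

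Under V2 to V10, 2 of the 6 endpoints have no scheduled pair. For ffERG both ends are missing. For OCT only the baseline is missing.

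**Step 2: does another provision supply the missing values?**
- The note under Table 1 lets the investigator repeat Screening Visit B tests at an unscheduled visit. ERG and OCT are not Visit B tests, so it does not help.
- Footnote 6 of Table 1 assigns V2 results to the quantitative analysis. It is attached only to BCVA, LLVA, DAC and MAIA. The schedule thus already treats ffERG and OCT differently, and 9.2.6 does not follow it.
- The looser sentence on change from the screening level could admit V1, which is Screening Visit A. That would give OCT a baseline. It would not give ffERG a Week 16 value, as the V1 to V10 column shows.

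**Step 3: perimetry.** Sections 2.2.2 and 6.7.5 define DAC perimetry as sensitivity in dB, for two stimuli, over 103 points. No section defines an area of visual field. One could be derived from the DAC grid, but only with a threshold and a rule that the protocol does not give.

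**Step 4: what a V1 to V9 ffERG change measures.** V9 is Week 12. The last scheduled injection is at Week 8 in Cohort A and Week 10 in Cohort B.
- Cohort A: 12 − 8 = 4 weeks, or 28 days.
- Cohort B: 12 − 10 = 2 weeks, or 14 days.
- Table 1 gives V7, V8 and V9 windows of ±5 days each, so each interval can move by up to 5 + 5 = 10 days. The ranges are 18 to 38 days in Cohort A and 4 to 24 days in Cohort B.

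**Step 5: early stopping.** Under Section 3.6, a subject who stops treatment early completes the Week 16 visit at that time. The Week 16 list in Section 7.10 has no ERG. A subject who leaves by this route before V9 therefore has no ffERG value after V1. Section 4.4 continues follow-up for safety, but does not say that it includes ERG.

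**The case against.** The strongest reply is that the data exist and the label is wrong. That stands. ffERG is taken in both eyes at V1 and V9, and OCT at V1 and at four later visits. A reader might infer that the trial yields no ERG data, or that all ERG values are missing. The documents do not support that: only the V2 to V10 change is unavailable.

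A reader might also infer that the analyst is forced into a free choice of visits after seeing the data. For ffERG there is no such choice, because two scheduled values allow one change score. For OCT there is one pre-dose scan, and 9.2.6 already points to V10, so the only room left is V9 against V10. Sections 9.2.1 and 9.2.8 also let the SAP override the protocol, and 9.2.8 requires analyses beyond the SAP to be labelled post hoc. That is a real route to repair. It is not full protection, since open-label results can be seen before lock. No separate SAP text accompanies the protocol in the combined document, so what it says on this cannot be judged.

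The OCT part is the weakest, for the reasons in the second step of the working. The list in 9.2.6 is introduced as what the endpoints include, so an unnamed endpoint is not necessarily dropped. It would also go too far to say that perimetry has no defined scale: the endpoint section gives dB, and the fault is that 9.2.6 does not use it.

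Finally, the primary endpoint is safety and tolerability, summarised descriptively, and it does not depend on any of this.

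**Conclusion.** The ffERG mismatch is an error as written. The rule gives 0 of 8 scheduled pairs, and no other section repairs it. V1 to V9 gives up to 8 of 8. For OCT, V1 is the only scheduled pre-dose value, and 9.2.6 should say so instead of leaving it to the looser sentence. The visual field area matches none of the six endpoints and should go.

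This is a should-fix point. It concerns secondary endpoints, the needed data are collected, and the correction is wording. It does not show that the efficacy analysis as a whole fails: BCVA, LLVA, LLD, MAIA and DAC all have both visits.

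The counts assume 8 subjects who attend every visit as scheduled. Missed visits, early stopping, or DAC exams excluded for more than 20% false positives (Section 6.7.5) would lower them.

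**What to change.** Replace the single rule in Section 9.2.6 with rules by endpoint, and carry them into the SAP before efficacy data are reviewed:

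- **BCVA, LLVA, LLD, MAIA and DAC:** change from V2 to V10.
- **ffERG dark-adapted b-wave amplitude:** change from V1 to V9 (Week 12). State that this is nominally 4 weeks (Cohort A) or 2 weeks (Cohort B) after the last scheduled injection, subject to the visit windows.
- **OCT (CSFT and EZ):** change from V1 to V10. Name OCT in the list.
- **Perimetry:** replace "improvement in visual field area and microperimetry" with separate entries for MAIA and for change in DAC sensitivity in dB to the blue and the red stimuli, as in Section 2.2.2. Fix the summary over the test points in the SAP; the protocol does not give one.
- **Early stopping:** state that subjects who stop before V9 and complete the Week 16 visit at discontinuation will have no post-baseline ffERG, because that visit includes no ERG. Say how they are counted.

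The cost is wording in Section 9.2.6 and the SAP. No new assessments are needed.

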4.4. Handling of Subject Withdrawals or Subject Discontinuation of Clinical Trial Intervention

Subjects that are dropped from the clinical trial prior to administration of the interventional investigational product will be considered screen failures and will not be included in analysis.

Any subject receiving the investigational product will be followed for safety throughout the scheduled course of the clinical trial, or until the subject has reached a status of un-reachable. To assure the clinical trial meets the required approximate 8 evaluable eyes for analysis, additional subjects may need to be enrolled to meet this goal.

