6.7. Ophthalmic Examinations

6.7.1. Best-Corrected Visual Acuity

BCVA will be collected at Screening Visit A (V1), Screening Visit B (V2), and Visits V3, V5, V7, V9, and V10. The BCVA will be measured using ETDRS chart by masked technicians at a standard photopic light level of at least 85 cd/m². Both eyes will be examined at all time points.

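### Section 9.2.6 reads efficacy from change since screening alone and gives the untreated fellow eye no role, although BCVA, LLVA, ffERG and OCT are measured in both eyes

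*Combined protocol and SAP*

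**What the plan says.** Section 3.1 describes the design: "In this open-label, non-comparator Phase II clinical trial, 8 (eight) evaluable subjects", treated in the worse seeing eye only. Allocation is sequential: "The first four subjects (Cohort A) will be treated with monthly intravitreal injections", and the last four (Cohort B) receive twice-monthly injections. Section 2.1 lists efficacy beside safety as an objective. The primary endpoint is safety and tolerability, and the visual and structural measures are secondary.

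Section 9.2.6 sets the efficacy contrast as the change from V2 to Week 16 (V10): "Change from Screening level will be the dependent variable". It names no eye, model, comparator or reference. It lists BCVA or LLVA letters, visual field area, microperimetry and dark-adapted b-wave amplitude. OCT, a secondary endpoint in Section 2.2.2, is not in the list.

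The fellow eye is nevertheless measured. For BCVA, Section 6.7.1 says "Both eyes will be examined at all time points", and Section 6.7.2 says the same for LLVA. Section 6.7.4 has ffERG in both eyes at V1 and V9. For OCT, Section 6.7.6 says "Both eyes will be evaluated at visits V1, V9, V10". MAIA microperimetry and DAC perimetry are done in the study eye only (Sections 6.7.3 and 6.7.5). No endpoint or analysis section says what the fellow-eye results are for.

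**The concern.** Without a reference, the mean change in the injected eye estimates the drug effect plus everything else that moved between the two visits. For BCVA and LLVA that includes any learning left after the V1 test and a general rise in effort in an unmasked subject. For ffERG and OCT it includes device drift. For all of them it includes progression of a degenerative disease. The first group can imitate a benefit; progression can hide one. The fellow eye has the same subject, visits, devices and examiners, so its change carries whatever part of these influences is common to both eyes. At stake is how far the Section 2.1 efficacy objective can be answered. The primary safety assessment is not affected.

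**Working it through.** **Inputs.** n is about 8 ("To assure the clinical trial meets the required approximate 8 evaluable eyes for analysis", Section 4.4), in cohorts of 4 and 4 (Section 3.1). The level is two-sided 0.05 (Section 9.2.1). The documents give no effect size, SD, power, expected drift or between-eye correlation, so there is no plan figure to reproduce. Drift and correlation below are assumptions, in units of the SD of the change score. A one-sample t analysis is also assumed, because Section 9.2.6 names none.

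**Step 1: which paired contrasts the schedule allows (Table 1; Sections 6.7.1 to 6.7.6).**

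| Measure | Fellow eye measured at | V2 to V10 possible? | Usable window |
|---|---|---|---|
| BCVA, LLVA (hence LLD) | V1, V2, V3, V5, V7, V9, V10 | yes | V2 to V10 |
| ffERG | V1, V9 | no | V1 to V9 |
| OCT | V1, V9, V10 | no (no V2) | V1 to V10, and V1 to V9 |
| MAIA, DAC | never | no | none |

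The Section 9.2.6 window cannot be applied to ffERG or OCT even for the study eye.

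**Step 2: what each contrast estimates.** Let the mean study-eye change be δ + c and the mean fellow-eye change be c, with δ the drug effect and c the shift common to both eyes. Study-eye change estimates δ + c. The difference estimates (δ + c) − c = δ.

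**Step 3: false improvement with δ = 0, study-eye change only.** This is the chance that the 95% CI lies wholly above zero: P = 1 − F(t₀.₉₇₅; n − 1, d√n), where F is the noncentral t distribution function and d = c/SD. At n = 8 and d = 0.5, the noncentrality is 0.5 × √8 = 1.414 and P = 23.1%. At n = 4 it is 0.5 × √4 = 1.0 and P = 10.8%.

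| Shared upward shift (SD) | n = 8 | n = 4 |
|---|---|---|
| 0 | 2.5% | 2.5% |
| 0.25 | 8.9% | 5.6% |
| 0.5 | 23.1% | 10.8% |
| 0.75 | 44.9% | 18.6% |
| 1.0 | 68.1% | 28.9% |

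The rate is lower at n = 4 because the interval is wider, not because the bias is smaller. A downward shift of 0.5 SD at n = 8 gives 0.07% false improvement and 23.1% false worsening.

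**Step 4: the paired difference under the same 0.5 SD shared shift.** With 200,000 simulated trials of n = 8, false improvement is 2.5% to 2.6% and the two-sided rate 4.9% to 5.1%, for between-eye correlations r of 0, 0.5 and 0.8.

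**Step 5: precision.** SD of the difference = SD × √(2(1 − r)). The 95% CI half-width for study-eye change is t₀.₉₇₅/√n: 0.836 SD at n = 8 and 3.182/2 = 1.591 SD at n = 4.

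| r | Ratio √(2(1 − r)) | Half-width, n = 8 (SD) | Half-width, n = 4 (SD) |
|---|---|---|---|
| 0.3 | 1.18 | 0.99 | 1.88 |
| 0.5 | 1.00 | 0.84 | 1.59 |
| 0.7 | 0.77 | 0.65 | 1.23 |
| 0.8 | 0.63 | 0.53 | 1.01 |

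The difference is more precise than study-eye change only if r exceeds 0.5.

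**Step 6: does choosing the worse eye create a gain?** Simulated with assumed true between-eye SD of 3 to 12 letters and test error SD of 2 to 4 letters. If the eye were chosen on the same reading that serves as baseline, regression to the mean would add 0.3 to 2.0 letters to the study-eye change and 0.5 to 4.0 letters to the paired difference. If the eye is chosen at V1 and the baseline is V2, the study-eye bias is about zero. Table 1 marks MAIA and DAC at V1 as study eye only, so the eye must already be designated then, and it makes V2 the source for quantitative analysis. The schedule thus implies the harmless arrangement, but no sentence states it.

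**The case against.** A reader might infer that the fellow-eye data will never be used. The documents do not support that. Section 9.2.6 is brief, and Section 9.2.8 defers to a separate SAP that overrides the protocol and is not in the supplied text. What can be said is that this protocol assigns those data no role. The same section treats analyses outside the SAP as post hoc, which is a reason to specify the contrast before database lock.

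A reader might also infer that all non-drug change flatters the drug. It does not. V1 is a run-in test with V2 as baseline, and BCVA is taken by masked technicians, so practice and assessor effects are partly handled. Later learning and subject effort are not. Table 1 also permits V2 tests to be repeated at the investigator's discretion without saying which result counts. Practice and effort matter much less for ffERG and OCT. Natural history is decline, which works against an apparent gain.

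A third tempting inference is that selecting the worse eye builds in a spurious improvement. Step 6 shows that this belongs to a scenario the schedule argues against.

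Two objections stand as limits on the remedy. The fellow eye is the better eye, so it is not fully exchangeable and may have a different ceiling. The subject knows which eye was injected, so eye-specific effort survives the subtraction. MAIA and DAC, the most effort-dependent tests, are not helped at all. Finally, the n = 8 figures pool two regimens, and Section 9.2.6 does not say that the cohorts will be pooled for efficacy.

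**Conclusion.** The point holds in a limited form. In an open-label trial without a comparator, Section 9.2.6 gives no means of separating drug effect from change common to both eyes, while data that would do so for four measures are already being collected. The consequence could be material: a shared gain of 0.5 SD with no drug effect takes false improvement from 2.5% to about 23% at n = 8, or about 11% within one cohort, and the paired difference returns it to about 2.5%. These rates rest on an assumed shift, a t analysis and a shift equal in the two eyes. Nothing in the documents shows that a shift of this size is likely, or in which direction the net effect would run. Efficacy is secondary, so the point limits what can be concluded about benefit and leaves the primary safety aim untouched. The paired contrast is supportive and does not turn the fellow eye into a full control.

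**What to change.** In Section 9.2.6, or in the SAP before database lock:

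- Beside the study-eye change, report the within-subject difference (study-eye change minus fellow-eye change) with its 95% CI as a supportive analysis, by cohort and pooled.
- Use the windows the schedule allows: BCVA, LLVA and LLD from V2 to V10; ffERG from V1 to V9; OCT from V1 to V10, and also to V9. Add OCT to the endpoint list.
- Name the eye to which the main change analysis applies. State that the study eye is fixed at V1 and that the acuity baseline is V2, and say which result counts if V2 tests are repeated.
- Label MAIA and DAC changes as uncontrolled and descriptive.

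The cost is a few lines of text and a few extra tables; no test, visit or subject is added. Because the interval is wider when the between-eye correlation is below 0.5 and the eyes are not fully exchangeable, both results should be shown and neither should replace the other.
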